7.2. Method of Treatment Assignment

Patients who meet all criteria for enrollment will be randomized in a 1:1 ratio (MP-101:placebo) to double-blind treatment at Visit 2 (Week 0). Assignment to treatment arms will be determined by a computer-generated random sequence using an interactive web-response system (IWRS). The IWRS will be used to assign blister packs containing double-blind investigational product to each patient. Blister packs will be dispensed at Visits 2, 4, 5, and 6, (Weeks 0, 2, 4, and 6, respectively). During the patient's visit, the site will access the IWRS for the correct blister pack numbers to dispense.

Randomization will be stratified by baseline MMSE score and eGFR value:

- MMSE < 16 or MMSE > 16
- eGFR <60 or eGFR > 60

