10.1. Sample Size Determination

Approximately 100 patients will be enrolled to enable approximately 80 evaluable patients to complete the study through at least Visit 5 (Week 4). The sample size was chosen so that there is at least an 80% chance the trial will show a statistically significant improvement in the response rate on the NPI-Psychosis scale (hallucinations plus delusions scores) and/or on the NPI-agitation/aggression domain in patients treated with MP-101 compared to placebo. This assumes a true response rate of 65% in the MP-101 treatment group versus 35% in the placebo treatment group, using a one-sided Fisher's exact test with a 5% type 1 error rate.

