10.3. Statistical Analyses

10.3.1. General Statistical Considerations

Statistical analysis of this study will be the responsibility of Mediti Pharma, Inc. or its designee.

Details of the summarization and analysis of the clinical trial data will be described in the SAP, which will be finalized prior to database lock.

The primary analyses will be performed with patients grouped by treatment arm (i.e., MP-101 or placebo) regardless of their final dose level.

The sample size was calculated assuming a 20% drop-out of patients in each arm, and assuming that early withdrawal is not influenced by the treatment effect. Secondary and supportive analyses may be performed to explore the effect of early withdrawal on the primary endpoint.

Pharmacokinetic analyses will be conducted on data from all patients on MP-101. Safety analyses will be conducted for all treated patients, whether or not they completed all protocol requirements.

Additional exploratory analyses of the data will be conducted as deemed appropriate.

A change to the data analysis methods described in the protocol will require an amendment only if it changes a principal feature of the protocol. Any other change to the data analysis methods described in the protocol or SAP, and the justification for making the change, will be described in the clinical study report.

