## **1.4.** Sample Size Determination

Approximately 100 patients will be enrolled to enable approximately 80 evaluable patients to complete the study through at least Visit 5 (Week 4).

The primary analysis will use a one-sided Fisher's exact test with a 5% type 1 error rate.

If the NPI response rate in MP-101 treated patients is 30% greater than in placebo treated patients (65% vs 35%), with 40 evaluable patients per treatment group there is at least an 80% chance (i.e. Power) that MP-101 will demonstrate superiority to placebo.

The sample size was calculated assuming an expected 20% drop-out rate of patients in each arm prior to Week 4, so that 100 patients are planned to be enrolled to arrive at 40 patients/arm (N=80) in the Evaluable population.

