#### **NPI Response**

Patients whose response to treatment cannot be determined due to missing data (including early withdrawal) will be considered non-responders.

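### SAP 1.4 claims at least 80% power, but exact Fisher power at 40 per arm is 79.5%, and the plan states no allowance for withdrawals after Week 4 that can be scored as non-response

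*SAP*

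**What the plan says.** SAP 1.4 sets the test: "The primary analysis will use a one-sided Fisher's exact test with a 5% type 1 error rate". For response rates of 65% and 35% it states that "with 40 evaluable patients per treatment group there is at least an 80% chance (i.e. Power) that MP-101 will demonstrate superiority to placebo". Protocol 10.1 makes the same power claim and describes its inputs as a "true response rate of 65% in the MP-101 treatment group versus 35% in the placebo treatment group".

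SAP 1.4 goes from 80 evaluable to 100 enrolled patients by "assuming an expected 20% drop-out rate of patients in each arm prior to Week 4". Protocol 10.3.1 gives the same percentage without a time point ("The sample size was calculated assuming a 20% drop-out of patients in each arm") and adds that early withdrawal is taken to be independent of the treatment effect.

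The primary analysis uses the Evaluable population (protocol 10.3.3.1). Under protocol 10.2 and SAP 2.3, a patient enters it by completing Week 4 with the relevant NPI score at Week 4 or later. Leaving after that does not remove the patient. The protocol synopsis places the response comparison at the end of treatment. For missing responses, SAP 2.7 (NPI Response) states: "Patients whose response to treatment cannot be determined due to missing data (including early withdrawal) will be considered non-responders".

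**The concern.** Two things do not fit together. First, the power is stated as a minimum, so it should hold when computed with the planned test, and it has no reserve if it does not. Second, the sample-size section and the analysis rule treat loss differently. A patient lost before Week 4 leaves the analysis and is replaced by enrolling more. A patient lost after Week 4 stays in the denominator and, if response cannot be determined, counts as a failure. The second kind of loss has no stated allowance.

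Such losses are foreseen. The protocol takes patients out of the study for intolerance after Week 4 (7.4), for noncompliance (7.6), and for rescue therapy or excluded medication (7.7). Six of the ten treatment weeks come after Week 4.

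At stake is how a non-significant result is read. The sponsor would set it against a stated power of at least 80%, when the planned rule may give several points less.

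**Working it through.** **Inputs from the documents.** One-sided Fisher's exact test, alpha 0.05 (SAP 1.4); response rates 0.65 and 0.35 (SAP 1.4, protocol 10.1); 1:1 allocation (protocol 7.2); 40 evaluable per arm; 20% drop-out before Week 4 (SAP 1.4).

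**Input not in the documents.** The share w of evaluable patients who withdraw after Week 4 and are scored as non-responders. It is an assumption and is shown as a range.

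**Step 1: enrolment.** 80 / (1 − 0.20) = 100. This agrees with the plan.

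**Step 2: the plan's power.** Let X₁ and X₂ be the numbers of responders, with X₁ ~ Bin(n, p₁) and X₂ ~ Bin(n, p₂). The test rejects when the hypergeometric tail probability P(X₁ ≥ x₁ | x₁ + x₂) is at most 0.05. Power is the sum of Bin(x₁; n, p₁) × Bin(x₂; n, p₂) over all rejecting pairs.

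- n = 40, 0.65 vs 0.35: 0.795
- n = 41, same rates: 0.811

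The stated figure is therefore reproduced to within half a point but not as a minimum. A normal-approximation sample size with continuity correction (one-sided 5%, 80% power) returns exactly 40 per arm. That is a plausible source of the number, though the documents do not name their method.

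**Step 3: later withdrawal, if 65% and 35% are rates before the non-responder rule.** With loss equal in both arms and unrelated to response, each rate becomes p × (1 − w), at 40 per arm:

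| w | MP-101 | Placebo | Difference | Power |
|---|---|---|---|---|
| 0% | 65.0% | 35.0% | 30.0 points | 79.5% |
| 2.5% | 63.4% | 34.1% | 29.3 points | 77.5% |
| 5% | 61.8% | 33.3% | 28.5 points | 75.3% |
| 10% | 58.5% | 31.5% | 27.0 points | 70.8% |

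These losses come on top of the 20% already lost before Week 4. At w = 10%, total loss is 1 − 0.80 × 0.90 = 28%.

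**Step 4: 20% total loss spread evenly over 10 weeks.** Of 50 per arm, 10 are lost, 4 of them by Week 4 and 6 later. That leaves 46 evaluable per arm, of whom 6/46 = 13.0% are scored as failures. The rates become 0.65 × 40/46 = 56.5% and 0.35 × 40/46 = 30.4%. Power at 46 per arm is 77.8%.

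**Step 5: unequal loss at 40 per arm.**

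- 5% on MP-101, 10% on placebo (61.8% vs 31.5%): 80.3%
- 10% on MP-101, 5% on placebo (58.5% vs 33.3%): 64.9%

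**Step 6: if 65% and 35% are already net of the rule.** Nothing is subtracted and power stays at 79.5%. At 10% later loss, the rates before the rule would then be 0.65 / 0.90 = 72.2% and 0.35 / 0.90 = 38.9%.

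**The case against.** A reader might infer that the plan assumes nobody withdraws after Week 4, and that the design therefore fails to deliver its stated power. The documents do not support that.

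- **The rates may be net.** SAP 1.4 speaks of the NPI response rate, and under SAP 2.7 that rate counts undetermined patients as failures. Calling the rates true, as protocol 10.1 does, only names the population value and does not mean before imputation. On the net reading, later leavers need no separate allowance. This stands, but neither document says which reading is meant.
- **No Week 4 to Week 10 rate is given.** Its balance between arms and its link to response are not given either. If withdrawal follows worsening in patients who would have failed anyway, scoring them as failures costs nothing. Step 5 shows that the effect can go either way. This stands and makes the size conditional. Equal, unrelated loss is a reasonable base case because it is close to the working assumption in protocol 10.3.1.
- **Not every later leaver is necessarily a failure.** The NPI is scheduled at the early termination visit, and SAP 2.7 applies only where response cannot be determined. However, SAP 5.2 carries early termination data forward only for the mixed model of quantitative endpoints, and SAP 2.7 expressly includes early withdrawal. The point is unclear and not resolved in the plan's favour.
- **Half a point is small.** Both documents give approximate patient numbers, and 41 evaluable in one arm with 40 in the other gives 83.3%, because power of the exact test moves in steps. This is fair as to importance. It does not make the claim as printed, for 40 per arm, correct.
- **Further analyses are possible.** Protocol 10.3.1 allows analyses of the effect of early withdrawal. They would not correct the stated power.

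**Conclusion.** The point holds in two parts of different strength.

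The first is unconditional. On the plan's own inputs, exact power is 79.5%, so at least 80% is missed by 0.5 points.

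The second is conditional. The plan states no allowance for withdrawal between Week 4 and Week 10, and it does not say whether 65% and 35% are rates before or after the non-responder rule. If before, and if later loss is equal and unrelated to response, power is 77.5% to 70.8% for 2.5% to 10% loss, or about 78% if 20% total loss is spread evenly. If after, it remains 79.5%. Unequal loss can move power in either direction.

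This is a gap in what the plan states, not proof that the trial is underpowered.

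**What to change.** In SAP 1.4 and protocol 10.1:

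1. Replace at least 80% by 79.5% (about 80%), and name the calculation as exact power of the one-sided Fisher test at 40 per arm.
2. State whether 65% and 35% are rates before or after undetermined responses are counted as failures.
3. If before, report power over a range of withdrawal after Week 4, for example 79.5% at 0%, 77.5% at 2.5%, 75.3% at 5% and 70.8% at 10%, with the assumption of equal loss unrelated to response written beside it.

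It would also help if SAP 2.7 said whether an NPI score from the early termination visit can determine the primary response, since this decides how many later leavers the rule affects.

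The cost is wording only. The stated figure becomes slightly less favourable; sample size and test do not need to change.

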# 2. GENERAL STATISTICAL METHODOLOGY AND CONVENTIONS

## 2.1. General Considerations

All computations for statistical analyses will be performed using SAS® software, Version 9.4 or later. All SAS programs used in the production of statistical summary outputs will be validated with independent programming prior to finalization. In addition, all program outputs will be independently reviewed. The validation process will be used to confirm that all data manipulations and calculations were accurately done. Once validation is complete, a senior statistical reviewer will perform a final review of the documents to ensure the accuracy and consistency with this plan and consistency within tables. Upon completion of validation and quality review procedures, all documentation will be collected and filed by the project statistician or designee.

Before implementation of parametric methods of analysis, the distribution of analysis variables will be examined to determine if model assumptions are satisfied. Transformations or nonparametric methods of analysis may be used if warranted. However, in some cases, nonparametric analysis may be the initially proposed method due to the expected distribution of response. Whenever alternative methods of analysis are required, the description of the new method along with the rationale for its use will be documented in the Clinical Study Report (CSR).

Data listings will be sorted by treatment group, investigative site, and patient identification number, and patients will be identified in the listings by the investigator number concatenated with the patient number.

Some patients were enrolled under protocol MP-101-01(a). These patients completed the Cohen-Mansfield Agitation Inventory questionnaire, Alzheimer's Disease Cooperative Study - Activities of Daily Living Inventory, and Alzheimer's Disease Cooperative Study - Clinical Global Impression of Change. These questionnaires were removed from MP-101-01(b). Data from these questionnaires will not be included in tables, listings, or figures but SDTM/AdAM datasets will be created. For the remaining instruments, assessments were discontinued at some visits. Data collected at these visits will be included in listings, but summary tables will only include the scheduled assessments under the current protocol.

## 2.2. Randomization and Unblinding Plan

Cenduit LLC will be responsible for the system that randomly assigns study treatments to patients. Assignment to treatment arms will be determined by a computer-generated random sequence using an interactive web-response system (IWRS). Randomization will be stratified by baseline MMSE score and eGFR value:

- MMSE < 16 or MMSE  $\ge$  16
- $eGFR < 60 \text{ or } eGFR \ge 60$

Members of the Assessment Committee and unblinded teams will gain access to unblinded data, prior to the final database lock, in order to perform the interim analyses. Information that may unblind the study during the analyses will not be reported to study sites or blinded study team members (including Mediti Pharma, Inc. personnel) until the study and all data management activities have been completed at the end of the trial, unless there is information study sites need to know for the safety of their patients. Members of the Assessment Committee or unblinded teams will not disseminate any information derived from its privileged access to the data without the prior written approval of Mediti Pharma, Inc.

The investigator may determine that unblinding of a patient's treatment assignment during the trial is warranted for medical management of the patient. However, if it is decided that unblinding is warranted, every effort should be made to contact the Chorus clinical research physician (CRP) prior to unblinding a patient's treatment assignment unless this could delay emergency treatment of the patient. If a patient's treatment assignment is unblinded for the investigator, Chorus must be notified immediately and the patient must be discontinued from the study, unless the investigator obtains specific approval from the Chorus CRP for the study participant to continue in the study. Emergency unblinding to the investigator for adverse events may be performed through the IWRS, which may supplement or take the place of emergency codes generated by a computer drug-labeling system. This option may be used ONLY if the patient's ultimate well-being requires knowledge of the patient's treatment assignment.

Analyses will not include patient's data collected after the time of unblinding. Sensitivity analyses that include these data may be performed depending on how much of this data there is.

Cenduit LLC is responsible for making the randomization file available to the unblinded interim analysis team at EMB Statistical Solutions. After the last patient completes the study and all data management

data activities have been completed – data entered, coding completed, and all queries resolved – the Chorus Asset Manager or designee and Study Statistician will approve the unblinded interim analysis reporting team at EMB Statistical Solutions to release the randomization schedule.

A list of individuals who become unblinded prior to study completion will be maintained by the Assessment Committee chairperson, the Asset Manager, and/or the unblinded statistician at EMB Statistical Solutions and will be placed in the final Study Trial Master Files.

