7.3. Blinding

Blinding will be maintained throughout the conduct of the trial until all data are verified to an acceptable level of quality and locked.

Select individuals may gain access to unblinded data prior to the final database lock to initiate the final population PK model development. The individuals and unblinded data will be specified in the unblinding plan section of the Statistical Analysis Plan (SAP) or a separate unblinding plan document.

If, in the opinion of the investigator or the Mediti Pharma, Inc. clinical research physician (CRP) or designee, unblinding of patients is necessary for the management of adverse or other clinically relevant events, the patients' treatment code will be made available.

Emergency unblinding for AEs may be performed through the IWRS, which may supplement or take the place of emergency codes generated by a computer drug-labeling system. This option may be used ONLY if the patient's well-being requires knowledge of the patient's treatment assignment. All unblinding events are recorded and reported by the IWRS.

If an investigator, site personnel performing assessments, or patient is unblinded, the patient must be discontinued from the study. In cases where there are ethical reasons to have the patient remain in the study, the investigator must obtain specific approval from a Mediti Pharma, Inc. or designated CRP for the patient to continue in the study.

In case of an emergency, the investigator has the sole responsibility for determining if unblinding of a patient's treatment assignment is warranted. Patient safety is the primary consideration in

making such a determination. If the investigator decides that unblinding is warranted, the investigator should make every effort to contact the Mediti Pharma, Inc. CRP prior to unblinding, unless a delay compromises patient safety. If a patient's treatment assignment is unblinded, Mediti Pharma, Inc. must be notified immediately.

Upon completion of the study, all codes must be returned to Mediti Pharma, Inc. or its designee.

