## 6. SAFETY ANALYSES

All analyses of safety including the extent of exposure to study medication will be performed using the Safety population.

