## 6.2. Adverse Events

Investigators will monitor the safety of patients and will be responsible for their medical care during the study. The investigator will interpret and document clinically significant signs and symptoms along with any change in conditions and will indicate whether each event is serious or otherwise medically important, considered related to the study medication, or if it caused the patient to discontinue the study medication before completing the study. The patient will be followed until the event resolves, stabilizes with appropriate diagnostic evaluation, or is reasonably explained.

No statistical testing will be performed for comparisons of AEs.

Summaries of AEs will include the number of patients with at least one AE for each treatment group. When reporting by system organ class (SOC) and preferred term (PT), the reports will present the SOC in alphabetical order; while PTs within the SOC will be presented in order of overall decreasing frequency of occurrence in the MP-101 treatment group. A patient with multiple AEs (different PTs) coded to the same SOC will be counted only once for that SOC, but will be counted each time for different PTs within that SOC. A patient with separate events of the same PT (different start/stop dates) will be counted only once in the frequency tables for that PT.

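### SAP 2.2 drops data collected after unblinding from analyses without exempting safety, in conflict with the SAP's own safety rules

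*SAP*

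**What the plan says.** **The exclusion.** SAP 2.2, part of the general methodology section, says: "Analyses will not include patient's data collected after the time of unblinding". It continues: "Sensitivity analyses that include these data may be performed depending on how much of this data there is". No endpoint, threshold or safety output is named.

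**Why codes are broken.** The same section says "Emergency unblinding to the investigator for adverse events may be performed through the IWRS", and limits this to cases where the patient's well-being depends on knowing the treatment. Protocol 7.3 describes the trigger as cases where "unblinding of patients is necessary for the management of adverse or other clinically relevant events".

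**What follows for the patient.** SAP 2.2: "the patient must be discontinued from the study, unless the investigator obtains specific approval from the Chorus CRP".

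**The safety rules.** SAP 6: "All analyses of safety including the extent of exposure to study medication will be performed using the Safety population". SAP 2.3 defines that population as everyone randomized who took at least one dose. SAP 6.2 counts as treatment-emergent every event that starts or worsens after first dose, and provides for a listing of every death if any treatment-emergent event is fatal. SAP 6.5 takes all QTcF values on treatment into the extreme-value counts, unscheduled ones included. None of these rules mentions unblinding.

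**Follow-up and the protocol.** SAP 6.2 says of adverse events: "The patient will be followed until the event resolves, stabilizes with appropriate diagnostic evaluation, or is reasonably explained". Protocol 10.3.1 says: "Safety analyses will be conducted for all treated patients, whether or not they completed all protocol requirements". SAP 1.1 gives the SAP precedence over the protocol's statistical sections where they differ.

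**The concern.** Dropping ratings made with knowledge of treatment is reasonable for caregiver- and clinician-rated scales such as the NPI, CGI-I and ZBI-22. That reason does not carry over to deaths, serious events, laboratory values or ECGs. The rule nevertheless covers them, because it is written for analyses in general.

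The patients affected are not a random subset. Their codes were broken because something clinically relevant had happened, so the records removed are likely to be the continuation of the more worrying events. Safety and tolerability is a stated secondary objective (Protocol 4.2; SAP Table 1), and in a trial of about 100 patients one serious event can change how a table reads. The optional sensitivity analysis is least likely to be run when few codes are broken, which is when a single event carries most weight.

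**Working it through.** The plan attaches no figure to this point, so there is none to reproduce. The check is one of text, followed by simple arithmetic.

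**1. Does anything in section 6 limit the cut?** No. The Safety population settles which patients are counted, not which of their records. Sections 6.1 to 6.6 contain no sentence keeping data collected after unblinding.

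**2. Can such records exist?** Yes, by four routes:
- follow-up of known adverse events (SAP 6.2; Protocol 9.2);
- follow-up information on serious events (Protocol 9.2.1);
- the early termination visit that sites try to obtain (Protocol 8.2), at which adverse events, ECG, chemistry and hematology, and C-SSRS are scheduled;
- patients approved to continue after unblinding.

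TUG is not scheduled at early termination, so later TUG values would come mainly from patients who continue.

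**3. The rules side by side.**

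| Output | Rule in SAP section 6 | Effect of 2.2 read literally |
|---|---|---|
| TEAEs (6.2) | every event emerging or worsening after first dose | event first recorded after the code break is not counted |
| Maximal severity (6.2) | worst grade across a patient's TEAEs | later escalation is missed and the lower grade stands |
| Serious TEAEs (6.2) | summarized by arm | a change to serious recorded later is missed |
| Deaths (6.2) | every death listed; summary table optional | conflict; a fatal outcome recorded later could leave a summary count |
| TEAEs leading to discontinuation (6.2) | identified from the drug-withdrawal action | that action may be recorded after the code break, since unblinding normally ends participation |
| Extreme QTcF (6.5) | all on-treatment values | conflict for a patient still dosed after unblinding |
| Laboratory, TUG (6.3, 6.6) | descriptive statistics by time point | later values are missing |

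**4. Timing.** The cut depends on when data are collected, not on when the event began. An event that starts before the code break but is entered afterwards is also caught by the literal wording.

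**5. Size.** Inputs: 100 patients to be enrolled (SAP 1.4) and 1:1 allocation (SAP 1.1). Assuming nearly all are dosed, each arm has 100 / 2 = 50 treated patients. If *u* patients in one arm have an event of a given type first recorded after unblinding, and none of that type before, the reported incidence is too low by 100 × *u* / 50 percentage points:
- *u* = 1: 2 points
- *u* = 2: 4 points
- *u* = 3: 6 points
- *u* = 5: 10 points

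The values of *u* are assumptions. The documents give no expected number of code breaks.

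**The case against.** The case against a serious reading is substantial, and most of it stands.

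- **Much is kept.** Unblinded patients stay in the Safety population. The event that prompted the code break is normally recorded first and therefore counted. The exposure is limited to what is recorded later.
- **Little may follow.** Most unblinded patients leave the study, and Protocol 9.2.1 does not oblige investigators to go on seeking events after that. The extreme-QTcF count covers time on treatment only, so a discontinued patient adds almost nothing to it.
- **Section 6 can be read the other way.** A programmer might let the specific rules on TEAEs, deaths and QTcF override a general sentence in the randomization section. This is fair, and it means deletion is likely on the literal text but not certain. It also shows that the SAP gives two answers and leaves the choice to whoever writes the program.
- **The protocol does not clearly conflict.** Its commitment to all treated patients concerns who is analyzed, and the SAP uses the same set. For the same reason, that commitment does not protect individual records.

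Three stronger readings are tempting but not supported. A reader might infer that the data disappear from every analysis; in fact a sensitivity analysis including them is permitted, although not promised. A reader might infer that a death could be lost to the study; serious events must be reported within 24 hours and deaths are to be listed, so the risk is to a summary count. A reader might infer that the rule makes MP-101 look safer; that would require more code breaks with later events on MP-101, and nothing in the documents indicates this.

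**Conclusion.** The point holds as a defect of scope and consistency. SAP 2.2 states a general exclusion that, followed as written, takes safety records made after a code break out of the main summaries, and it is not reconciled with sections 6.2 and 6.5. The amount lost is probably small. On the assumption of about 50 treated patients per arm, it is 2 percentage points of incidence in that arm for each patient whose event is first recorded after unblinding. The number of such patients and the direction of any bias are unknown. The primary endpoint is not affected by this point. It is worth correcting before the final analysis because the stated rule gives the wrong result for safety and the correction is nearly free.

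**What to change.** Replace the exclusion sentence in SAP 2.2 with:

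> Efficacy analyses (NPI, CGI-I, MMSE, ZBI-22) will not include data collected after unblinding of the patient, caregiver, investigator or rater. All safety analyses, including Section 6 and UPDRS Part III, will include all data regardless of unblinding; records collected after unblinding will be flagged in the listings.

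MMSE is named because it is an exploratory efficacy endpoint in SAP Table 1. UPDRS Part III is named because Table 1 makes it a safety endpoint while section 6 does not mention it, so its handling would otherwise stay open.

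The cost is a short change of SAP wording and one flag in the listings, with no new data collection. The downside is that relatedness judgements and UPDRS ratings made after unblinding may be influenced by knowledge of the treatment. The flag makes those records visible to the reader.
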